#### 2a. Research Plan

## 2a.1. Background and Significance

#### PTSD: Relevance to VA and to Treatment

The prevalence of posttraumatic stress disorder (PTSD) among Veterans is at least twice as high as in the general population. Vietnam Veterans exhibit a lifetime prevalence of PTSD at approximately 30%. Estimates of PTSD among Iraq and Afghanistan combat Veterans (Operation Enduring Freedom, Operation Iraq Freedom, and Operation New Dawn; OEF/OIF/OND) suggest that nearly 17% of active duty and over 24% of reserve service members screen positive for PTSD approximately 6 months after their return.

PTSD has been linked to poor health outcomes and is associated with enormous health care costs. Several large-scale studies conducted with combat Veterans have compared those with and without PTSD, and found that Veterans with PTSD report significantly more chronic health conditions and generally poorer perception of physical health than their non-PTSD counterparts, even when controlling for behaviors known to independently contribute to poor health outcomes such as smoking, alcohol use, deployment status, military status, and demographics. PTSD is associated with increased risk of early mortality, attempted suicide, functional impairment, alcohol abuse and dependence, reduced quality of life, psychiatric comorbidity, and hospitalization.

Prolonged exposure (PE) is an efficacious treatment for Veterans with PTSD that decreases avoidance of feared, but safe, cues to allow fear extinction and habituation to over-generalized feared stimuli. Although PE is one of the best available treatments for PTSD, PE still has high partial and non-response rates with 25 to 45% of PTSD patients still meeting diagnostic criteria for PTSD at the end of treatment. Given the high number of individuals who continue to have PTSD following PE, efforts to increase the efficacy of PE are critical. Independent comorbid disorders, such as insomnia, have been posited as one reason for the high non-response rates to PE. Examining how to increase efficacy of PE by focusing on comorbid insomnia offers a novel and logical approach to improve insomnia, PTSD, and quality of life outcomes.

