Study Name: Integrated CBT-I and PE on Sleep and PTSD Outcomes (Impact Study)

Document Name: Statistical Analysis Plan

NCT ID: NCT02774642

Document Creation Date: 11-20-2015

PI: [name]

Planned Data Analysis 11-13-2015

Power analyses: Sample size was determined to ensure adequate statistical power to detect between group differences in PTSD and sleep at end of treatment and 3-month follow-up. For both outcomes the effect size was estimated as d defined as $[d = |m_1 - m_2| / \sigma]$ where m_1 and m_2 are change from intake in the outcome scores of the two conditions and σ is the common within-group standard deviation of the change score.¹⁰⁹ The effect size for the between group difference in PTSD CAPS scores from intake to end of treatment was estimated from several studies that have evaluated the effect of PE^{110, 111} on PTSD. Four studies of PE have demonstrated large within group effect sizes ranging from 1.3¹¹¹ to 4.1¹¹² with an average ES of 2.5. However, given that both conditions will receive PE, and it is already known that CBTI shows large effects on insomnia (e.g., Ulmer⁸⁰ ES = 2.15), we powered on the effect of CBTI on PTSD symptoms.

Three studies reported effect sizes of CBTI on PTSD symptoms with an average ES of 1.8.⁷⁹⁻⁸¹ We conservatively used a large effect size (0.8) requiring 34 participants per group to be detected with 90% power and a two-tailed test with alpha at .05. We increased the total sample size to be randomized to $N = 90$ in anticipation of 25% study drop-out by the 3 month assessment. Overall, we believe this sample size balances three needs: (1) sufficient power to compare the study groups; (2) the reality of recruiting a sample with dual insomnia and PTSD; and (3) project cost considerations.

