Data Analysis. Preliminary analyses will consist of examining the descriptive statistics of the study sample. Outliers will be assessed and variables whose distributions depart significantly from normality will be transformed. Internal consistency of scales will be examined to determine reliability. *All analyses will be run with the full, validated PTSD scales (e.g., CAPS and PCL5) and with sleep items removed from the PTSD scales.*

Primary Aim 1 (Treatment outcomes): Investigate the efficacy of CBTI-PE on PTSD, sleep, and quality of life among Veterans with co-occurring PTSD and insomnia.

Hypothesis Aim 1: Veterans who receive CBTI-PE, compared to Hygiene-PE, will demonstrate lower PTSD symptoms, better sleep efficiency, and better quality of life at follow-up.

Independent variables: Treatment group (CBTI-PE versus Hygiene-PE) and Time (Baseline 0 weeks, Post-treatment 14 weeks, Follow-up 28 weeks).

Dependent variables (three separate models): CAPS-5 scores, Sleep Diary Sleep Efficiency, WHOQOL-BREF.

Covariates: gender, age, medications, pain, depression.

Analyses Aim 1: Analyses of this data will be conducted using three separate Random Regression Models, a generalized linear model described by Gibbons et al.⁸⁶, Hedeker et al.¹¹⁴, and Laird et al.¹¹⁵ The random effects method has several advantages over more traditional analytic approaches such as a change score, end-point, or repeated measures ANOVA. This method allows the inclusion of subjects with missing data or those who were terminated early in the study, without relying on data imputation procedures. This method provides an

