estimate of the individual variability around the population trend, the variability of the individual intercepts (baseline values) and slopes (changes across time), and the correlation between them. The model will include a random intercept, a random effect for assessment time, and fixed effects for comparison groups and group-by-time interaction. A fully saturated treatment by time model will be utilized for inference. Co-variance structure will be chosen based on Akaike's Information Criterion (AIC) and *compared to each other using a chi-square test*. Random group level treatment effects will also be evaluated for importance based on the model AIC. This allows for any group level effects to be incorporated into the model. Data will be analyzed from all randomized subjects using all available data collected at baseline, post-treatment, and at follow-up. The models will be expanded to determine an adjusted intervention difference by including additional covariates such as *gender, age, medications, pain, and depression*. A chi-square test will compare attrition rates between groups.

Secondary Aim 2: Examine the effects of sleep efficiency on PTSD outcomes at post-treatment.

Hypothesis Aim 2: *All Veteran's CAPS-5 scores will decrease from pre- to post-treatment.* However, Veterans who demonstrate larger increases in sleep efficiency will exhibit lower PTSD symptoms at the end of treatment compared to Veterans with lower sleep efficiency.

Independent variables: Sleep Efficiency (sleep diary) at week 6, *Pre-treatment CAPS-5 scores*

Dependent variables: CAPS-5 scores at post-treatment.

Covariates: *age, gender, medications, pain, depression.*

Analyses Aim 2: A multivariate regression equation will be used to statistically test this hypothesis. Regression analyses will be used to examining the relationship between SE at week 6 on follow-up CAPS-5 scores controlling for pre-treatment CAPS-5 scores. A significant finding for SE will indicate that Veterans who are sleeping more efficiently at week 6 of treatment has an additive influence on the effectiveness of PE.

Secondary Aim 3 (Moderator): Determine the extent to which SE and changes in PTSD symptoms relate to global quality of life outcomes.

Hypothesis 3: *There will be an interaction effect of SE at post-treatment and changes in PTSD symptoms from pre- to post-treatment predicting quality of life outcomes.*

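### The SAP's mandatory transformation of non-normal variables does not exempt the primary outcomes, so the scale of the primary estimates is left to the trial data

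*SAP*

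**What the plan says.** The rule is in the opening paragraph of the SAP's Data Analysis section, among the preliminary analyses. After a statement that outliers are to be assessed, it says that "variables whose distributions depart significantly from normality will be transformed". The same section lists the outcomes for Aim 1: "Dependent variables (three separate models): CAPS-5 scores, Sleep Diary Sleep Efficiency, WHOQOL-BREF".

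The SAP does not say which test or threshold defines a significant departure, or which transformation follows. It does not say whether raw values or residuals are checked, whether arms and visits are pooled, whether the check is blind to arm, or how a transformed effect is reported.

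One nearby sentence might look like an exemption: "All analyses will be run with the full, validated PTSD scales (e.g., CAPS and PCL5) and with sleep items removed from the PTSD scales". It concerns which items enter the PTSD score, not the scale on which the score is analysed.

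For inference, Analyses Aim 1 says: "A fully saturated treatment by time model will be utilized for inference". The power paragraph defines the effect size d through "change from intake in the outcome scores of the two conditions", divided by a sigma that "is the common within-group standard deviation of the change score". Aim 3 uses change in CAPS-5 and its interaction with sleep efficiency.

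**The concern.** The wording is mandatory, the trigger is each variable's own distribution, and nothing excludes the primary outcomes. A linear mixed model does not require a normal marginal outcome. Its distributional assumption concerns residuals once arm and visit are in the model. A marginal distribution can look non-normal simply because means differ between visits or arms, or because patients respond differently. The protocol itself expects a mixed response to prolonged exposure (PE), with "25 to 45% of PTSD patients still meeting diagnostic criteria for PTSD at the end of treatment" (section 2a.1). Sleep efficiency is also bounded at 100%.

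At stake is the meaning of the primary result. A group-by-time contrast on a root, log or logit scale is not a difference in CAPS-5 points or sleep-efficiency points. It is also not the change-score difference on which d was defined. The Aim 3 interaction is scale-dependent too: an interaction can appear or vanish under a monotone transformation. The choice of scale would be made after seeing the data.

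**Working it through.** **Plan's own figure.** For d = 0.8, two-sided alpha 0.05 and 90% power, a two-sample t-test needs 33.83, so 34 per group (power 0.902 at 34). With 25% drop-out, 68 / 0.75 = 90.67, against the stated 90. The plan's figure reproduces. It rests on a change score in outcome units.

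**Assumption for everything below.** The trigger is taken as a Shapiro-Wilk test at 5% on raw values, because the SAP names no test. All percentages are simulated.

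**Sleep efficiency.** Inputs: pilot diary means (SD) of 73.30 (8.65) before and 91.07 (6.24) after treatment, from three Veterans (protocol section 2a.2). A beta distribution is matched by k = m(1 − m)/s² − 1, a = mk, b = (1 − m)k.

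- Before: k = 0.733 × 0.267 / 0.0865² − 1 = 25.16; a = 18.44, b = 6.72; skewness −0.40.
- After: k = 0.9107 × 0.0893 / 0.0624² − 1 = 19.89; a = 18.11, b = 1.78; skewness −1.20.

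| Sample | Flagged, n = 34 | Flagged, n = 68 |
|---|---|---|
| Before treatment | 11% | 20% |
| After treatment | 77% | 98–99% |

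With one arm at the before level and one at the after level, pooled (34 + 34), 95% are flagged.

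**CAPS-5.** The documents give no mean, SD or shape, so only a range can be shown.

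| Assumed distribution | Flagged |
|---|---|
| Two normal arms of 34 pooled, no effect | 5.1% |
| Same, design effect 0.8 SD | 4.7% |
| Baseline (90), post (68) and follow-up (68) pooled, common shift 1.3 SD | 6.4% |
| Same, shift 2.5 SD (the SAP's average PE effect) | 85% |
| Post only (68), 25% or 45% unchanged, others shift 1.3 SD | 6% or 4% |
| Same, shift 2.5 SD | 40% or 21% |
| Same, shift 4.1 SD (top of the SAP's range) | 99.7% or 98% |
| Responders 12 (SD 7), non-responders 33 (SD 8); 25, 35, 45% non-response; negatives set to 0 | 95, 85, 67% |
| Responders 15 (SD 9), non-responders 33 (SD 10); same rates; negatives set to 0 | 49, 37, 21% |

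**Type I error.** In the 12-versus-33 mixture the raw t-test holds 4.9–5.3%. With a gamma outcome matched to the pilot post-treatment PCL-5 (15.33, SD 8.62) and 34 per arm, it is 4.4% raw and 4.3% if a square root is applied when flagged. It is 5.6% if the smallest p of raw, root and log is taken when flagged.

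**Power, raw / root / log.** The direction depends on how benefit arises.

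- 12-versus-33 mixture, non-response cut from 40% to 10%: 64 / 52 / 39% with negatives set to 0. True truncation softens the loss to about 56% (root) and 46% (log). This effect is about d = 0.57, not 0.8.
- Same mixture at 35% non-response, responders' mean lowered by 6 points: 14 / 20 / 28% with truncation, about 19 / 34 / 45% with negatives set to 0. The order reverses.
- Gamma outcome, effect 0.8 SD: 89.8% raw, 93.4% with the root rule.

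**What a change of scale does to the estimate.** The pilot means differ by 91.07 − 73.30 = 17.77 points. Applied to the means, this is ln(0.9107/0.0893) − ln(0.7330/0.2670) = 2.32 − 1.01 = 1.31 on a logit scale. On a reflected root scale it is √8.93 − √26.70 = 2.99 − 5.17 = −2.18, with the sign reversed. The SAP does not say which would be reported.

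**The case against.** The sentence is common boilerplate, listed among preliminary analyses, and could be read as a residual check. Validity is barely touched, and a transformation sometimes gains power. All of this stands except the residual reading: the text refers to the distributions of variables.

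Four stronger readings are tempting, and the documents do not support them.

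- **Effective treatment would itself force CAPS-5 off its scale.** At the design effect of 0.8 SD the flag rate is 4.7%, against 5.1% with no effect. High rates need large PE shifts or widely separated responder groups. The claim holds as *could* for CAPS-5 and *probably would* for sleep efficiency.
- **Transformation costs power.** That follows only if benefit comes from moving patients out of the high-scoring group. Under other mechanisms the ordering reverses.
- **Baseline could stay raw while follow-up is transformed, so that change no longer exists.** The SAP treats CAPS-5 as one dependent variable with Time as a factor. The natural reading is one transformation for the whole outcome.
- **Outliers will be removed.** The SAP says only that they will be assessed.

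**Conclusion.** The point holds in limited form: a mandatory, data-triggered rule, keyed to the wrong distribution, can change the scale of the primary outcomes. That conclusion follows from the text and needs no simulation.

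The likelihood is well supported only for diary sleep efficiency: about 98–99% flagged at n = 68 after treatment, against 20% before. This rests on a beta shape, moments from three Veterans and an assumed 5% Shapiro-Wilk test. For CAPS-5 the range of about 5% to over 95% mainly shows that the documents do not settle it. No flag rate was calculated for WHOQOL-BREF; the rule simply reaches it.

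The harm is to prespecification, to interpretability in outcome points, and to the link with the power calculation and the Aim 3 interaction. It is not a material inflation of type I error or a predictable loss of power. Severity: should-fix.

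**What to change.** Replace the transformation sentence with a rule along these lines:

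- CAPS-5, diary sleep efficiency and WHOQOL-BREF are analysed on their original scales at all visits for primary inference.
- Residuals from the fitted mixed models are inspected; raw marginal distributions do not determine the scale.
- If residuals are poor, robust or bootstrap standard errors are reported as a sensitivity analysis. Optionally, one transformation per outcome, named in advance and applied to every visit, is added as a further sensitivity analysis.

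The cost is SAP wording plus one sensitivity run, and possibly slightly lower power where a transformation would have helped. The sample size stays at 34 per group and 90 randomized, because d is already defined on the untransformed change score.

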If the Veteran meets eligibility criteria based on baseline assessment, the Veteran will then be randomized into either CBTI-PE or the control condition Hygiene-PE. Veterans will be given a sleep diary to compete for 7 days to prospectively record sleep measures (e.g., "lights out," time to fall asleep, time spent awake during the

night, total sleep time, and "lights on") and be given an actigraph (a wrist watch device) which they will wear continuously for the 7-day baseline evaluation.

**Treatment Randomization:** Following baseline assessment, participants will be randomized to the intervention (CBTI-PE) or control condition (Hygiene-PE). A computer-generated randomization sequence will be provided by our statistical expert [name] (consultant), and held by a colleague not otherwise involved with the study. Randomization will be stratified by gender to ensure a balanced number of males and females are in each treatment group.

**Bi-Weekly Assessment** (approximate time = 10 minutes): During treatment, brief self-report assessments will be given every other week when the patient arrives for therapy to track quality of life, sleep, and PTSD symptoms. Additional measures will include adherence to assignments and satisfaction with treatment.

**Post-treatment Assessment** (approximate time = 2 hours): In the week following completion of the final treatment module, Veterans will be given a sleep diary to fill out for 7 days to prospectively assess sleep at post-treatment. Patients will also wear an actigraph during the post-treatment week so as to provide objective measures of sleep to compare with the subjective sleep diary reports. At the end of the post-treatment evaluation week Veterans will return to the VASDHS to turn in the diary and actigraph and will at this time be administered the same battery of clinical assessments originally given during the baseline evaluation visit.

**3-Month Follow-Up Assessment** (approximate time = 2 hours): Veterans will return to VASDHS to do the same battery of clinical assessments they completed at baseline and post-treatment. At the conclusion of the assessment, Veterans will have completed the study. Veterans who are randomized to the control condition and who are interested in receiving the standard CBT-I treatment will be provided with CBT-I treatment at the completion of their participation in the study.

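### Gender is the only stratification factor, but the SAP does not commit it to the Aim 1 model used for inference: a minor, conservative loss of efficiency

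*SAP*

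**What the plan says.** Protocol section 2a.3.f, under Treatment Randomization, states: "Randomization will be stratified by gender to ensure a balanced number of males and females are in each treatment group". It describes the sequence only as computer-generated. It gives no block size or other restriction within strata.

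The Aim 1 part of the SAP says three things that bear on gender:

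- The Aim 1 covariate line puts gender first: "Covariates: gender, age, medications, pain, depression".
- The Aim 1 model has a random intercept, a random effect of assessment time, and "fixed effects for comparison groups and group-by-time interaction". The next sentence is: "A fully saturated treatment by time model will be utilized for inference".
- Later in the same paragraph: "The models will be expanded to determine an adjusted intervention difference by including additional covariates such as" gender, age, medications, pain and depression.

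The SAP does not label either the base or the expanded model as primary, and it does not identify gender as the stratification factor.

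**The concern.** Stratifying by gender makes the arms similar in gender mix. If men and women change by different amounts, that similarity removes part of the chance variation in the difference between arms. A model that omits gender still counts this variation as residual error. Its reported SE is then larger than the true sampling SD of the estimate, its intervals are too wide, and its test rejects less often than the nominal 5% under the null.

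The wording of the SAP makes this possible. The statement about inference is attached to the treatment-by-time model, and gender comes in only when that model is expanded. The expanded model is also an awkward place for the stratifier. Its list is open-ended. It combines gender with pain, depression and medications, which protocol Table 5 also schedules during or after treatment, and the SAP does not restrict them to baseline values. The plan therefore offers no estimate adjusted for the stratification factor alone.

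**Working it through.** **1. The plan's own figure.** Inputs from the SAP power section: "We conservatively used a large effect size (0.8) requiring 34 participants per group to be detected with 90% power", two-sided alpha 0.05, with the SD defined as the within-group SD of the change score. A two-sample t-test calculation gives 33.83, so 34 per group, with power 0.9015 at 34. The stated 34 reproduces. With 25% drop-out, 68/0.75 = 90.7, so 91 against the stated 90, which is close enough.

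**2. What matters for the contrast.** The group-by-time contrast compares changes from baseline. With complete data, a constant gender difference cancels from each person's change. Only a gender difference in change (gender-by-time) can affect the SE.

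**3. Formulas.** Let p be the proportion of women and g the gender difference in change, in units of the within-gender SD. With exact balance within gender:

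- v = p(1 − p)g², and the share of change-score variance due to gender is R² = v/(1 + v).
- Unadjusted SE divided by true SE = 1/√(1 − R²) = √(1 + v).
- True two-sided level = 2[1 − Φ(1.96 √(1 + v))].

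**4. Results.** The documents give neither p nor g for this trial, so both are assumptions. The 11% row follows the only gender split I find in the documents (preliminary Study 4, 89.1% male), which is a different sample.

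| p | g | v | R² | SE too large by | True level |
|---|---|---|---|---|---|
| 0.25 | 0.3 | 0.0169 | 1.7% | 0.8% | 4.8% |
| 0.25 | 0.5 | 0.0469 | 4.5% | 2.3% | 4.5% |
| 0.25 | 0.8 | 0.1200 | 10.7% | 5.8% | 3.8% |
| 0.11 | 0.3 | 0.0088 | 0.9% | 0.4% | 4.9% |
| 0.11 | 0.5 | 0.0245 | 2.4% | 1.2% | 4.7% |
| 0.11 | 0.8 | 0.0627 | 5.9% | 3.1% | 4.3% |

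Example, p = 0.25 and g = 0.5: v = 0.25 × 0.75 × 0.25 = 0.0469; √1.0469 = 1.023; 1.96 × 1.023 = 2.005, which gives a level of 0.045.

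**5. Simulation check.** Change scores were simulated under the null with N = 68, 15,000 runs per setting, and assumed shares of 12% and 30% women.

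- With exact balance within gender, the unadjusted test rejected in 0.042 to 0.052 of runs for R² from 0 to 6.3%, and in 0.034 at R² = 11.9%. The gender-adjusted test stayed at 0.047 to 0.052.
- With simple randomisation and no balancing, the unadjusted test stayed near nominal (0.045 to 0.053).

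**6. Power at 34 per group, d = 0.8.** Both models are compared under balance with the same normal approximation. The noncentrality is 0.8/√(2/34) = 3.298. Unadjusted power is Φ[(3.298 − 1.96)√(1 + v)] and adjusted power is Φ[3.298√(1 + v) − 1.96]. With p = 0.25 and g = 0.3, 0.5 and 0.8, unadjusted power is 0.912, 0.915 and 0.922, and adjusted power is 0.914, 0.922 and 0.937. The difference is roughly 0.3 to 1.5 percentage points. The required sample size does not rise.

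**The case against.** The strongest reply is that gender is already in the Aim 1 plan. It heads the covariate list, and the SAP says the models will be expanded with it, so that analysis is planned and not optional. The phrase about a saturated model can also be read as describing only how treatment and time are parametrised, with no trend imposed across visits and no statement about covariates. This stands to the extent that a reader cannot say the plan ignores gender, or that the unadjusted result is declared primary. It does not settle the matter. Gender is described as one of the additional covariates that expand the model, so the natural reading is that the inferential model lacks it, and nothing in the SAP makes the adjusted result the primary one.

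A second reply is that the harm is conditional. The protocol describes no blocking, and without effective balance within gender the test stays near nominal; drop-out can loosen balance further. The documents report no gender difference in change, and the 0.8 SD case assumes one as large as the treatment effect used for sample size. All of this stands and limits the point to a small one.

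A reader might go further and infer that the primary analysis is invalid, or that the benefit of stratifying is lost. The documents support neither. Any error is conservative, and the protocol's stated purpose, balanced numbers of men and women in each arm, is met whichever model is fitted.

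**Conclusion.** The point holds as a minor one. The SAP does not say which Aim 1 model is primary, and it does not place its only stratification factor in the model it attaches to inference. The sizes shown for 25% women are assumed-scenario figures. They rest on four things the documents do not establish: that the unadjusted model is the one used, that balance within gender is achieved, the proportion of women, and a gender difference in change. They were also derived for complete-data change scores, not for the mixed model with missing visits. If any of the first, second or fourth conditions fails, the loss shrinks or disappears. The consequence is a modest loss of precision and power, not a threat to the validity of the trial.

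**What to change.** Add one sentence to the Aim 1 analysis: for CAPS-5, diary sleep efficiency and WHOQOL-BREF, the primary model is the saturated treatment-by-time model with gender and gender-by-time included because gender is the stratification factor. The interaction is needed, since a gender main effect alone would barely change the SE of a change contrast. State that the model with age, medications, pain and depression added is a secondary adjusted analysis.

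This needs no further data or participants. With three visits and a two-level factor it uses three fixed-effect parameters (one for gender, two for gender-by-time), which is negligible with 90 randomised. It should be settled before outcome data are examined by arm.

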**Integrated Treatment (CBTI-PE):** The integrated treatment uses the core components of CBT-I and PE, with the goal of enhancing both insomnia and PTSD outcomes. Integrated treatment will be delivered in 14 90-minute weekly sessions. CBTI-PE (see Table 3 for full outline of protocol) starts with VA rollout CBT-I for the first 3 weeks with a focus on the effects of PTSD on insomnia. PE protocol (psychoeducation) begins on week 4 of treatment and both treatments overlap till week 6 when CBT-I ends and the active treatment of PE begins (i.e., imaginal and in-vivo exposures). However, CBT-I sleep diary review and sleep time adjustment will continue till the end of treatment to increase adherence to the sleep schedule. The timing of integrated treatment will allowing appropriate time for CBT-I to influence sleep efficiency before PE exposures start. Final session 14 includes reviewing goals from treatment, discussing progress and concrete skills to be used post-treatment, and discussing relapse prevention and handling reemergence of insomnia or PTSD symptoms. The integrated manual was developed and piloted with two subjects (see Preliminary Studies 2a.2) diagnosed with comorbid insomnia and PTSD at the VASDHS.

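### Aim 2 adjusts only for week-0 PTSD severity, so PTSD improvement before exposures that moved with sleep can be credited to sleep enhancing PE

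*SAP*

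**What the plan says.** **Model.** The SAP (Analyses Aim 2) describes a regression "examining the relationship between SE at week 6 on follow-up CAPS-5 scores controlling for pre-treatment CAPS-5 scores". The listed outcome is "CAPS-5 scores at post-treatment", so I take the word follow-up in that sentence to mean post-treatment. The other covariates are "age, gender, medications, pain, depression", with no measurement time given. No PTSD score later than week 0 enters as a predictor.

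**Inference rule.** The closing sentence of Analyses Aim 2 takes a significant SE term to show that sleeping well at week 6 adds to what PE achieves.

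**Timing.** Protocol 2a.3.g explains the integrated sequence as "allowing appropriate time for CBT-I to influence sleep efficiency before PE exposures start". In Table 3 (CBTI-PE), weeks 1–3 have no PE content, weeks 4–5 hold psychoeducation and the trauma interview, in-vivo homework starts in week 6, and the first imaginal exposure is in week 7. The Actigraphy paragraph of 2a.3.i also treats week 6 as the week before imaginal exposures. Table 4 (Hygiene-PE) says only that the PE protocol runs in weeks 4–14.

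**Expected early change.** SAP, Power analyses: "Three studies reported effect sizes of CBTI on PTSD symptoms with an average ES of 1.8".

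**Available data.** Table 5 has no CAPS-5 at week 6 but lists the PCL-5 as bi-weekly. Section 2a.3.f confirms that "brief self-report assessments will be given every other week when the patient arrives for therapy to track quality of life, sleep, and PTSD symptoms".

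**The concern.** The predictor is placed at the start of exposures, while the severity adjustment sits about six weeks earlier. Any PTSD change in between stays in the outcome. A Veteran whose PTSD eased by week 6 may sleep better that week and also finish with a lower CAPS-5, even if sleep does nothing for exposure therapy. The reverse direction, PTSD relief improving sleep, leaves the same trace, and the protocol's own preliminary work (Study 5) suggests that PTSD and insomnia symptoms may drive each other.

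Three explanations therefore give the same SE coefficient: sleep made PE work better, PTSD was already lower when exposures began, or early PTSD relief improved sleep. The SAP's inference rule names only the first. That is the mechanism the conceptual model proposes, so a wrong reading would matter beyond this secondary aim.

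**Working it through.** **1. The plan's own figure.** No sample size or power is given for Aim 2. The Aim 1 figure reproduces. The normal approximation is n = 2(1.960 + 1.282)² / 0.8² = 32.8, so 33 per group; the noncentral t gives 34 (power 0.9015). Then 68 / 0.75 = 90.7, so 91 against the stated 90. Conversely 90 × 0.75 = 67.5, so I use N = 68. Protocol 2a.3.b states about 52 at follow-up, which I use as a second case.

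**2. Set-up.** On the scale left after adjusting for week-0 CAPS-5 and the five covariates, with no effect of week-6 SE on later PTSD change:
- r1 = size of the (negative) correlation of week-6 SE with week-6 PTSD severity. Assumed, 0 to 0.5.
- r2 = correlation of week-6 PTSD with post-treatment CAPS-5. Assumed, 0.5 to 0.7.
- ρ = reliability of the week-6 PTSD score. Assumed, 0.7, 0.8 or 1.

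**3. Planned model.** The SE term then has an expected partial correlation of −(r1 × r2). The chance of p < 0.05 is approximately Φ(atanh(r1·r2)·√(n − 3) − 1.96), plus a small opposite tail. Here n = 62 if the six adjustment terms are charged and n = 68 if not.
- r1 = 0.2, r2 = 0.5, n = 62: 0.1003 × 7.681 = 0.771; Φ(−1.189) = 0.117, plus 0.003, gives 12%.
- r1 = 0.2, r2 = 0.7, n = 68: 0.1409 × 8.062 = 1.136; Φ(−0.824) = 0.205, plus 0.001, gives 21%.
- r1 = 0.5, r2 = 0.7, n = 68: 0.3654 × 8.062 = 2.946; Φ(0.986) gives 84%.

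**4. Model with a week-6 PTSD score added.** The remaining partial correlation is −r1·r2(1 − ρ) / √[(1 − r1²ρ)(1 − r2²ρ)].
- r1 = 0.3, r2 = 0.5, ρ = 0.8: −0.15 × 0.2 / √(0.928 × 0.8) = −0.035, about 6%.
- r1 = 0.5, r2 = 0.7, ρ = 0.8: −0.35 × 0.2 / √(0.8 × 0.608) = −0.100, about 13%.

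**5. Simulation** (10,000 replicates per setting, six terms charged, r2 from 0.5 to 0.7; chance of a significant SE term):

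| r1 | Planned, N = 68 | Planned, N = 52 | Week-6 score added, ρ = 0.7, N = 68 | ρ = 1, N = 68 |
|---|---|---|---|---|
| 0 | 5% | 5% | 5% | 5% |
| 0.2 | 12–18% | 10–15% | 6–7% | 5% |
| 0.3 | 22–38% | 17–29% | 7–9% | 5% |
| 0.5 | 50–80% | 39–68% | 11–19% | 5% |

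Leaving the six terms uncharged raises the upper ends at N = 68 to 21% (r1 = 0.2) and 84% (r1 = 0.5), which gives the overall ranges 12–21% and 22–84%.

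**6. Is this only the absence of a treatment-arm term?** I let arm alone drive the co-movement (assumed week-6 PTSD difference d = 0.8, SE difference d = 1.0 to 2.0, r2 = 0.7, N = 68). The SE term is significant in 17–34% of trials without an arm term and about 5% with one. With a within-arm correlation of 0.3 as well, the arm term leaves about 41%; adding week-6 severity brings it to about 7%.

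**The case against.** **The aim is broader than the inference sentence.** The aim and hypothesis are worded around post-treatment PTSD and pre-to-post change, and week-0 CAPS-5 is the natural adjustment for that. This stands. A reader might infer that the planned model is simply wrong, but it is a sound estimate of a total association. Only the sentence about PE outruns it.

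**Week-6 adjustment can over-adjust.** Sleep restriction starts in week 2. If better sleep lowers PTSD by week 6, the week-6 score lies on that pathway. This also stands, and is why the planned model should be kept. But an effect of sleep on PTSD before exposures is not an effect on what exposures achieve.

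**The cited early effect is an arm effect.** CBT-I lowering PTSD would be removed by an arm term, as step 6 confirms. Co-movement within arm would not be, though no passage quantifies it.

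**Depression and pain could stand in.** The PHQ-9 is bi-weekly and pain is measured at week 6. If those values were used they would absorb part of week-6 severity, but the SAP does not say which time point enters. Removing sleep items from the PTSD scales deals with item overlap, not with severity at exposure onset.

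**A stronger reading on timing.** A reader might infer that all change up to week 6 precedes PE. It does not: PE content starts in week 4, and only exposures wait until weeks 6–7. Even that is documented session by session for CBTI-PE alone.

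**Conclusion.** The concern holds for the stated inference rule. With PTSD severity adjusted only at week 0, improvement before exposures that moved with sleep can be credited to sleep enhancing PE. The documents do not support saying that it will be: the bias requires week-6 SE and PTSD to be correlated given baseline, and no such correlation is reported.

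With N = 68, no true effect and r2 of 0.5 to 0.7, the false-positive rate runs from about 5% at r1 = 0, through 12–21% at r1 = 0.2, to 22–84% at r1 = 0.3 to 0.5. A week-6 score of reliability 0.8 reduces the last range to about 6–13%. These are illustrations under assumed correlations, not estimates for this trial. The week-6 score reduces the bias without abolishing it, and SE remains a non-randomized predictor in either model.

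**What to change.** 1. Keep the planned Aim 2 model, but report its SE coefficient as the association of week-6 SE with total pre-to-post PTSD change.
2. Prespecify a second model that adds the PCL-5 total at week 6, or at the nearest bi-weekly assessment before the first imaginal exposure, alongside pre-treatment CAPS-5. Run it with the full scale and with sleep items removed, as the SAP already plans elsewhere.
3. Make any statement about PE from the second model only, worded as an observational association.
4. State that one bi-weekly PCL-5 falls at week 6.
5. Reconcile the start of exposures in Hygiene-PE (Table 4) with the Actigraphy paragraph of 2a.3.i, so that week 6 means the same treatment stage in both arms.

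The cost is SAP wording and one degree of freedom in the second model; no new measure or visit is needed. The second model does not count any effect of sleep on PTSD before week 6, which the first still reports.
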